13.6	Study Documents Online and Study Records	19
13.7	Data Management	20
14	Reporting of Results	20
14.1	Investigator.....	20
14.2	Sponsor.....	21
15	Withdrawal of Sponsor	21
16	Overview of Case Report Forms and Questionnaires available online	21

1 Registry Synopsis

Device(s):	All Cochlear devices, eligible for market release.
Study title:	Cochlear - Implanted Recipient Observational Study (Cochlear - IROS).
Participating sites:	Sites selected for voluntary participation in the observational study (Cochlear - IROS), using any Cochlear devices that are eligible for market release.
Study Duration per subject:	Two years follow-up from Baseline registration. Baseline registration online occurs just after the patient is implanted and prior to the first switch-on. Follow-up at 1 and 2 years is recommended to occur in parallel to routine Clinical evaluations. Evaluation at third year post implant follow-up is optional.
Start date	Dec 2011, with ongoing roll out to clinics and countries as languages become available for use. Review of study progress at regular annual intervals.
Number of subjects:	A minimum of 50 recipients per device. Several hundred subjects across device user groups and device configurations are aimed for enrolment in the study /registry.
Study/Registry Design:	
Prospective, longitudinal comparative repeated measures of benefits for implanted hearing impaired subjects, acting as their own intra-subject control, using a selection of subjective evaluation tools provided via an electronic platform for data entry and data collation within a secured environment. Longitudinal repeated evaluations commencing at Baseline (post-implant, pre-switch-on) and repeated annually for up to 3 years post implant.
 
Patient benefits will be compared to safety records for Cochlear devices eligible for market release gathered through post market surveillance. Inter-subgroup (to be classified by device use and configuration) comparisons of performance per assessment tool per interval shall be performed pending numbers of relative data sets.
 
Note: The registry platform is designed to support and sustain uniform data collection on unlimited number of prospectively implanted patients long term.

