The registry is aimed at collection of data for patients who have already made the decision together with their implant centre clinician for an implant device from the company Cochlear®.

Participating in the observational study for each clinic and patient is voluntary. Both the clinic and patient are free to electively remove themselves from participation in the registry at any time. Patients should be enrolled that meet the selection criteria without bias This will enable interpretation of the results and application for the implant population at large.

Clinics are asked to enrol newly implanted patients into the study in chronological order of implantation.

Enrolment should occur after implant and must be prior to the first switch-on of their implanted device.

- **All prospective implantees who are able to provide consent for their participation in the observational study or for whom consent is provided by their legal representative.**
- All prospective implantees awaiting their first switch on of their external device
- Children 10 years or older and in accordance with local regulations and product labelling.
- Implantees or carers who are physically and mentally-able to complete the questionnaires independently as self-administered and *not as an interview* are able to participate.
- Each patient is evaluated at or immediately prior to the first switch on to obtain **baseline responses related** to their hearing experiences and perception of quality of life in **their pre-implant hearing condition**. Standard clinical tools: the SSQ and HUI Mark III are available for use and non-standard questionnaires for Clinicians and Patients
- Each patient is to be followed up through routine clinical procedures and in parallel asked to complete the post-implant versions of the questionnaires at their 1st, 2nd and 3rd year(optional) follow-up appointment \pm 2 months of the expected time frame.
- Inter-group comparisons of outcome data require a minimum of 100 subjects per subgroup per device type and configuration (and of comparable age group) for data analysis and formal report of their HUI Mark III data at the 1st, 2nd and 3rd year (optional) post-implant compared to their preoperative baseline responses. Statistical comparisons will be made in accordance with the recommended analytical procedures as validated by HUI Inc, the developers of the questionnaires.

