7.2 Exclusion Criteria

- Individuals excluded from participation in a registry according to national or local regulations.

8 Subject Identification and Confidentiality

In accordance with patient privacy laws, subjects will be identified anonymously on all evaluation forms and subsequently in the database only by a unique coded reference number that is automatically assigned by the database. This consists of the study number (assigned by Cochlear including the region managing the registry), country code, center code, and finally the patient specific code assigned in chronological order of implant at the clinic.

- Study number: Study specific **5277EU-**
- Country code: An abbreviation of the country name e.g. for Germany **GE**
- Center code: assigned by Cochlear for a specific clinic. e.g. clinic X in country Y - **02**
- Patient code: assigned automatically by the e-platform to indicate the chronological enrolment of patients at the clinic. E.g. the first patient enrolled is **-001**. No initials shall be included in the patient code which is centrally recorded. .

Example Patient Identifier code: 5277EU-GE-02-001

- The clinician will have the opportunity to include an identifier with 12 character spaces on the “*Clinician Baseline-Compulsory Form*” completed by the clinician. This will appear on the confidential patient listing for the clinic only.
- Should the patient move from the implant site where registered to another site any time after the registration for follow-up, the original clinic code defined by the system will be maintained.
- Clinicians will have the opportunity to transfer their registered implanted patient for follow-up via another participating site by completing the *Transfer patient form* online via the e-platform interface.

NOTE: Completed evaluation forms entered online or similar documents are confidential documents and will only be available to the Sponsor and their representatives, the clinic investigator, the investigational statistician, and if requested to the Ethics Committee. The name of any patient shall be kept confidential and shall not appear on any data forms, publication, or submission to regulatory authorities. Patients will be identified only by the subject code preserving anonymity.

9 Risk benefit analysis

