10.2 Investigational product traceability / recording

Registration cards for each implanted device are collected routinely for all implanted recipients receiving a market released **Cochlear** device and recorded through Cochlear’s post-market surveillance system following receipt from the clinic.

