11.3 Patient Informed Consent

The clinician is responsible for and must obtain written informed consent from each patient or their legal representative, prior to collecting any study data and formally enrolling them in the registry. This must occur after the patient is implanted when the decision for type and device configuration has already been taken independently to their decision to participate. Prior to obtaining their signature, verbal explanation and exchange must be provided to include:

- aims and objectives of study participation
- extent of the subject's involvement in terms of time, test intervals and tasks
- personal data privacy in printed material and electronic records
- their ability to cease their participation at any time during the course of the registry

The clinician is responsible to ensure that:

- all patients give written informed consent prior to enrolment in the registry through signing and dating the Patient Informed Consent form.
- a copy of the patient information sheet and consent form are given to the patient and the study details explained verbally.
- all signed patient informed consents are archived in the clinician's file at the centre/clinic, as per local requirements, and **at least for 5 years** after completion of the registry.

12 Data Reporting and Statistical Analysis

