13.5 Monitoring

There will be no routine on site monitoring of data entered. Participating clinics are not asked to store paper documents as source documents for data entered online; hence, no cross checks between data entered and source data is possible. Online spot-checks of recorded data to ensure quality assurance of data entered in terms of logic and ranges of data entered will be undertaken at random intervals and of randomly selected subsets of data during the course of the registry long-term. Data collected through observation of controlled market release of specific products may be subject to monitoring at regular intervals following prior agreement with the principal investigator for the defined period of the controlled market release. [REDACTED] for the Cochlear-IROS database, utilises an in-built audit trail for automated registration of all data entries and amendments by the authorised clinic personal and or patient.

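### Enrolment without bias is requested and used to support a claim about all implant recipients, but neither document lets anyone check it, and a rough denominator the sponsor collects is not used

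*Protocol*

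**What the plan says.** **The claim and its condition.** Protocol Section 6 gives the instruction "Patients should be enrolled that meet the selection criteria without bias" and follows it at once with "This will enable interpretation of the results and application for the implant population at large". It then asks clinics to enrol new recipients in the order in which they were implanted.

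**Who takes part.** The Protocol synopsis (Section 1) describes "Sites selected for voluntary participation in the observational study". Section 6 makes participation voluntary for clinic and patient alike.

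**When they enter.** Enrolment falls between implantation and first switch-on (Section 6), and the baseline evaluation may be up to 120 days after implantation (Section 6.1.1). Of consent, Section 11.3 says "This must occur after the patient is implanted"; its stated reason is that device choice should already have been made independently of participation.

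**What is recorded.** The patient code is "assigned automatically by the e-platform to indicate the chronological enrolment of patients at the clinic" (Section 8). The clinic's log lists those codes (Section 13.6). Section 13.5 states "There will be no routine on site monitoring of data entered" and provides random online spot-checks of the logic and range of entries.

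**What else the sponsor collects.** Section 10.2: "Registration cards for each implanted device are collected routinely for all implanted recipients receiving a market released" Cochlear device. The cards enter post-market surveillance once the clinic has sent them in.

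**The SAP.** Sections 1.3.3.2, 1.3.4.1 and 1.3.7 compare patients present and absent at follow-up. Section 2.3.1 reports 1361 baseline records.

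**The concern.** Section 6 makes application to all implant recipients depend on how patients are enrolled, yet nothing in either document measures how they were enrolled. A patient who was eligible but never registered leaves no trace: no gap in the code sequence, no line in the log, no form. Because registration follows surgery, the surgical course, the clinician's view of prognosis and the patient's willingness can all be known, and could affect who is registered.

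This matters because of the uses named in Sections 3, 5 and 14.2: support for clinical, reimbursement and regulatory decisions, and market communications. If enrolled patients differ in expected gain from those not enrolled, the mean HUI3 and SSQ changes describe a different population from the one that decision makers are told about, possibly to a different degree by clinic and device. More enrolment narrows the confidence interval but does not remove such a difference.

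**Working it through.** The plan states no figure for capture or selection bias, so there is none to reproduce. The check has two parts.

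**1. Could any planned record reveal a skipped patient?**

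| Record or check | Whom it covers |
|---|---|
| Patient code (Protocol 8) | Enrolled patients; codes follow on from one another whoever was skipped |
| Clinic log (13.6) | Patients with a code |
| Spot-checks and audit trail (13.5) | Data entered |
| End of study form (10.4) | Patients after registration |
| Case report forms (16) | Registered patients; none counts eligible, approached or refusing patients |
| SAP missing-data comparisons (1.3.3.2, 1.3.4.1, 1.3.7) | Enrolled patients, followed up or not |
| Registration cards (10.2) | All recipients whose card the clinic sent in; not linked to the registry in either document |

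Only the last row reaches beyond enrolled patients. Checking that enrolled patients are in implantation order would not help, since a sequence with omissions is still in order.

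**2. How large could the effect be? (illustration only)**

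Inputs from the SAP:
- Section 4.1.2.1, paired t-test of HUI3: mean gain 0.149, t = 5.966, df = 132, so n = 133. Implied SD of gain = 0.149 × √133 / 5.966 = 0.288.
- Section 1.3.1: pooled SD of HUI3 change 0.22; minimum important change 0.03.

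Inputs assumed, in neither document: enrolled fraction f, and correlation r between a normal enrolment propensity and HUI3 gain.

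*Propensity form.* Size of bias = r × SD × φ(z)/f, where z is the normal quantile of 1 − f.

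| f | φ(z)/f | r = 0.1, SD 0.288 | r = 0.3, SD 0.288 |
|---|---|---|---|
| 0.8 | 0.350 | 0.010 | 0.030 |
| 0.5 | 0.798 | 0.023 | 0.069 |
| 0.3 | 1.159 | 0.033 | 0.100 |

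This is 7% (0.010/0.149) to 67% (0.100/0.149) of the mean gain. With SD 0.22 the extremes are 0.1 × 0.22 × 0.350 = 0.008 and 0.3 × 0.22 × 1.159 = 0.076. A negative r gives the same sizes with the sign reversed.

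*Gap form, without r.* Bias = (1 − f) × (mean gain of enrolled − mean gain of eligible but not enrolled). The gap that produces a bias of 0.03 is 0.03/(1 − f):

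| f | Eligible patients behind 1361 records (1361/f) | Gap needed | Gap / 0.22 |
|---|---|---|---|
| 0.2 | 6805 | 0.0375 | 0.17 SD |
| 0.5 | 2722 | 0.06 | 0.27 SD |
| 0.7 | 1944 | 0.10 | 0.45 SD |
| 0.9 | 1512 | 0.30 | 1.36 SD |

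At low capture a small difference is enough; at 90% it would have to be implausibly large. Knowing f even roughly therefore tells the reader a good deal.

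*Sampling error for comparison.* SE = 0.22/√n: 0.031 at n = 50 (the Protocol's minimum per device) and 0.006 at n = 1361. The bias does not shrink with n.

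**The case against.** The strongest reply is that the plan asks for the right thing. It requests consecutive enrolment without bias, and the sentence about wider application gives the reason for that request rather than reporting something achieved. Voluntary sites and consent are inherent in a registry of this kind. Entry before switch-on rules out selection on device outcome. Consent after surgery has a sound reason. Incidents are reported for all market-released devices whether or not the patient is enrolled (Section 10.3). The SAP's formal tests concern the age-by-visit interaction and predictors of gain, not a population mean. The Data Management Plan (Section 13.7), the Registry Agreement (14.1) and the separate statistical report (12.1) were not available and might provide for tracking enrolment.

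Most of this stands and limits the point, but it does not supply a check on the request. Selection on prognosis, surgical course or willingness remains possible. The within-patient change is a primary end-point of the Protocol, whatever the SAP tests.

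A reader might go further in three ways that the documents do not support:
- *That clinics pick their patients.* Section 6 asks for the opposite; the defect is that compliance cannot be seen.
- *That there is no monitoring.* Section 13.5 excludes only the routine on-site kind, and allows for monitoring in controlled market releases. Its spot-checks simply cannot find a patient who was never entered.
- *That the sponsor already holds the eligible denominator.* The cards are per device, so a bilateral recipient may count twice. They depend on the clinic sending them, and they include recipients outside Section 7.1 (under 10, not post-lingually deafened, not first-time, unable to self-complete). The documents do not say which patient details the cards carry. They give a gross implant count.

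**Conclusion.** The point holds in this limited form. The Protocol rests a claim about all implant recipients on an enrolment request that neither document makes verifiable, and it leaves unused a gross count that would show roughly how complete enrolment was. This is a low-cost improvement to reporting and to the wording of a claim. It does not invalidate the analyses.

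The HUI3 range of 0.01 to 0.10 depends wholly on the assumed r and f, and its direction is unknown. It shows what would go unnoticed under the plan, not that any bias occurred. Even at the extreme, if the bias were upward, the gain would be 0.149 − 0.100 = 0.049, still above the 0.03 minimum important change though below the 0.1 that SAP Sections 1.3.1 and 4.1.2.1 treat as the change of interest. The conclusion covers the two documents only.

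**What to change.** 1. **Report capture.** In each report, give enrolments against registration-card counts by clinic, device and period, as aggregate counts. Count recipients rather than devices, and remove known ineligible recipients (for example under 10 years, or re-implants) where the cards allow. Label the result an approximate lower bound on capture of eligible patients: ineligible recipients left in the count push it down, while cards not sent in push it up.
2. **Reword the sentence in Protocol Section 6.** Conclusions apply to enrolled patients at participating clinics. Any wider application is stated as an assumption and shown beside the capture figures.
3. **Optionally, explore.** Show HUI3 and SSQ change by clinic capture. Do not set a fixed cut-off such as 80%: if half of a clinic's registrations were ineligible (assumed), perfect enrolment would still give 50%, so the cut-off would sort clinics by case mix. Do not treat agreement between high-capture clinics and the whole as permission to generalise, since all these clinics volunteered and the datasets overlap.

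Cost: a count from records already collected, one reworded sentence and, if wanted, one exploratory display; no new visits or patient burden. If the cards do not identify clinic and date, the rewording alone still corrects the claim. The downside is an approximate fraction and a more cautious statement.

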6.1 Evaluation Schedule

6.1.1 Subjective Evaluation schedule at routine clinic visits:

- Baseline Evaluation (This may be performed minimally on the implant date and maximally 120 days post implant and **MUST be prior to switch-on** of the external device)
- One year post-switch-on (implant day +12 months +/- 2 months)
- Two years post-switch-on (implant day +24 months +/- 2 months)
- Three years post-switch-on (optional currently (implant day +36months +/- 2 months))

6.1.2 Subjective Self Assessment Tools for completion by the Patient:

Together with the Clinician, self-evaluation tools to be completed by the patient are determined. The responsible clinician instructs the patient how to complete the forms. Each patient is asked to complete the selected self-assessment tools at each of the evaluation intervals noted above.

Completion of questionnaires/data entry may be performed by the patient pending their agreement on the signed Patient Informed Consent:

- on paper (as printed out from the host environment by the clinician) and then re-entered electronically by the responsible clinician in the clinic, or
- via direct on-line electronic data entry using their own access password provided by the e-platform **on a selected computer in the clinic** at the routine annual clinic visit
- via direct on-line entry using their own access password provided by the e-platform **pending the technical compatibility of their at home computer system and internet access (see section 13).**

(NOTE: For registered implanted recipients with visual impairment, having provided consent for their inclusion, all questionnaires may be administered verbally by the clinician or other and their responses recorded on paper or directly on line on their behalf).

Self-assessment Tools available for use

Two standardized internationally recognized clinical self-assessment subjective scales in conjunction with a general non-standard Patient questionnaire may be selected and completed by the implanted recipients at baseline and subsequently at annual evaluations.

The Speech, Spatial and Qualities of Hearing Scale (SSQ), a hearing-disease questionnaire. Established as a sensitive measure to demonstrate benefits of bilateral versus unilateral hearing ability in the a variety of daily situations and a range of hearing abilities as the title suggests. (e.g. Noble, Tyler et al. 2008) . Cross cultural version translations are validated. This questionnaire version has been assessed for self-assessment via self-administration from the age of 9 years. This questionnaire is designed and validated to be administered for prospective assessment of hearing ability.

The Health Utilities Index - Mark III (HUI3), a generic health status and health-related quality of life questionnaire. Established as a sensitive measure to demonstrate impact of medical treatments over time in 8 areas, (vision, hearing, speech, ambulation, dexterity, emotion, cognition and pain). Normative data is available. Evidence of its effectiveness as a useful tool to compare and demonstrate superiority of bilateral CI vs unilateral CI vs baseline pre-implanted status has been published to date (e.g. Bichey et al. 2008). It should be noted that strictly speaking this questionnaire is designed and validated for prospective assessment. Cross cultural validated versions have been licensed and made available for use in this study. This questionnaire version has been assessed for self assessment via self administration by individuals 6 years of age and older.

Implant recipient questionnaire, a non-standardised questionnaire (**2 versions: Baseline and Post implant evaluation**) designed to gather basic patient hearing history, degree of residual hearing pre and post-operatively, implant models and serial numbers, additional demographics and vocational aspects for each individual.

6.1.3 Evaluation forms for completion by the Clinician:

The clinician is trained on data entry procedures for Cochlear-IROS by Cochlear following agreement to participate voluntarily in the registry. Data entry is to be performed by the clinician directly or other staff member via direct on-line electronic data entry with access provided through use of their password on any suitable computer within the clinic during or coinciding with the timing for routine annual clinic visits occurring after one, two and three years (optional) post implant for the patient in question.

- **Clinician Baseline – Compulsory**, this form must be completed by the clinician with reference to each newly enrolled patient as it serves as registration of the patient at baseline evaluation. This is to ensure capture of the specific information related to technical details of the implanted device or devices and the external devices to be used, as well as any specific clinical technical details the patient does not have access to.
- **Annual Follow-up- Clinician (post implant: 1yr and 2yrs compulsory (and 3yrs optional))**. This is a general questionnaire that must be completed at an annual follow-up evaluation which coincides with routine annual clinic visit for the patient. This is to ensure capture of the specific information related to technical details of the implanted device or devices and the external

devices, and to reflect any changes that may have occurred over the preceding 12 months. Again it refers only to specific clinical technical details the patient does not have access to.

- **Product Specific procedures.**
- **End of study form** is also a compulsory form required to be completed by the clinician for each registered patient upon their departure from the registry either at the end of the prescribed set of evaluations, that is at 2 years or optionally 3 years post-implant or prematurely. A patient or clinician may choose to terminate participation in the registry prematurely at the individual wish of the patient or clinician or alternative following an event requiring removal of the patient from further review and data collection by the registry by default. The clinician is asked to record the reason for removal and date of exit from the study for each patient.
- **Unaided Hearing Threshold summaries.** The hearing threshold summary data recorded at baseline must reflect measurements performed prior to the implant surgery. Additionally, hearing thresholds measured immediately after surgery, in the period between surgery and before 1st switch-on or later) can be recorded at baseline evaluation. The evaluation form aims to capture a detailed summary of the pure tone hearing threshold levels that are routinely measured for the patient.
 1. **Pre-implanted hearing thresholds** routinely measured prior to the patients surgical procedure, for pure-tone stimuli via air and bone conduction in each ear for routinely measured frequencies between 125Hz and 8000 Hz) are required.
 2. **Immediately post-implant hearing thresholds.** At the clinic's discretion, the implanted patient's **hearing thresholds** if assessed immediately following surgery or up to some months later may be additionally recorded. This typically occurs either before the implanted patient is discharged from the implanting clinic after their surgery, or at the 1st switch-on of their device.
 3. **One year post-implant** (implant day +12 months +/- 2 months)
Two years post-implant (implant day +24 months +/- 2 months)

